#### 4. Research objectives:

The overarching objective is to determine efficacy of oral immunotherapy in peanut allergy. We will determine whether the planned intervention is successful in the intervention group compared to control (package 1),and whether it is successful when offered to the control group (package 2). Other objectives include identification of immunological changes over time, and improvement in quality of life scores.

#### 5. Research design

**5.1 Design.** This is a randomized controlled trial of a novel active intervention (peanut oral immunotherapy) versus the status quo (peanut avoidance) in 104 participants (7-18yrs) with peanut allergy (figure 1). One hundred and four participants will be recruited and undergo characterization by history, allergy testing, blinded peanut challenge and quality of life questionnaire. Peanut allergy will be confirmed in all participants by DBPCFC. Subjects are then allocated to either active or control group. Central minimization with weighting will be used to account for variation in severity of reaction (from history and challenge), peanut threshold dose (from challenge), age, sex, asthma, and allergies to other foods. After six-seven months subjects will undergo a DBPCFC (primary outcome measure). Subjects in the control group will receive current best management (a comprehensive management plan focusing on peanut avoidance) for six-seven months followed by DBPCFC. Those in the control group who still have a diagnosis of peanut allergy will be invited to undertake peanut oral immunotherapy followed by a final peanut challenge.

#### 5.2 Ongoing review

The Data Monitoring Committee (DMC) will review safety data on an ongoing basis and report to the TSC. The DMC may stop enrolment or participation in the trial at any moment if it concludes that there are significant safety concerns.

## 5.3 Stopping enrolment

Enrolment in the trial will be stopped pending review if any of the following occur

- Any death
- A participant is admitted to the intensive care unit for a study-related adverse event
- Any participant in the active treatment group experiences life-threatening anaphylaxis

## 5.4 Premature termination of trial interventions

Trial intervention will be prematurely terminated for a participant if, in the judgment of the investigator, further participation in the trial would be deleterious to the participant's health Participants will be prematurely terminated from the trial for either of the following: withdrawal of consent, or failure to return. Such participants will not be replaced.

## 6. Study population:

## 6.1 Inclusion criteria

1. Subjects aged between 7 and 15 years of age

2. Subjects with peanut allergy confirmed by a clinical history of a typical rapid onset immediate type hypersensitivity reaction to definite peanut ingestion.

3. Positive skin prick test to peanut (extract ALK-Abello, Hørsholm, Denmark) defined by weal ≥3mm in the presence of a negative control and positive histamine control.

4. Positive double blind placebo controlled food challenge performed according to international consensus guidelines

5. Informed consent obtained from parent / guardian or participant, as appropriate.

## 6.2 Exclusion Criteria

1. Clinically significant chronic illness, except for eczema, rhinitis or asthma.

- 2. Suspected or diagnosed allergy to peanut protein in care provider or current household member.
- 3. Unwillingness or inability to comply with study requirements and procedures.

**7. Planned interventions:** (see figure 1) All subjects will undergo initial clinical characterization by history and allergy testing (skin prick tests), and DBPCFC with peanut at study enrollment. DBPCFC will confirm clinical peanut allergy and identify the amount of peanut required to cause a reaction (threshold level).

#### 7.1 Peanut oral immunotherapy

Subjects randomized to the active intervention arm will receive daily doses of peanut protein starting at 1mg per day. This is given as peanut flour (50% protein) and is mixed into a carrier which is known to be tolerated (e.g. yoghurt). The first dose is administered on the Clinical Research Ward (CRW) followed by a 2 hour observation period. Subsequently this dose is taken daily at home by participants. Every 2 weeks subjects return to the CRW for a dose increase and 1 hour of observation. The dose increments are 1, 5, 12, 25, 50, 100, 200, 400 and 800mg. The final dose (or if this is not tolerated, the highest tolerated dose) is taken for at least six weeks until six-seven months post randomization when a DBPCFC is performed.

Provide each participating family with:

- Symptom advice sheet (containing advice to avoid strenuous exercise for 2 hours after home dose)
- Contact information (explain 24 hour contact system)
- Non-sedating oral antihistamine and injectable adrenaline device
- Training on adrenaline autoinjector use (provide trainer pen)

- Emergency treatment plan
- Subjects are asked to complete a symptom diary, noting type and duration of symptoms and any exacerbating factors (e.g. exercise, excessive tiredness, systemic illness).

If symptoms are experienced during updosing on the Clinical Research Ward then do the following:

- If wheeze / breathlessness / reduced PEFR / vomiting occur then provide the next lowest dose for daily active intervention. It should be noted that this action was not required in the pilot study. If the dose causing the reaction was the starting dose (1mg), then provide 0.5mg peanut protein for daily active intervention. Contact daily to reassess.
- If mild abdominal pain, oral itching or urticaria occurs then provide reassurance and continue the current dose. Contact daily to reassess
- If other symptoms occur that are intolerable to the subject that the dose can also be reduced at the investigator's discretion.

If any symptoms are experienced by participants at home, families are advised to contact the study team. Serious adverse events will be handled separately as below in section 9.

Make the following assessments and provide advice as indicated:

- If wheeze / breathlessness / vomiting occurs within 2 hours of a single dose taken at home then reduce the dose to the next lowest, and contact daily to reassess
- If abdominal pain / rhinitis / oral itching occurs within 2 hours of a single dose taken at home then continue with the current dose and contact daily to reassess
- If episodes of abdominal pain / rhinitis / oral itching occur every day for 10 days, then reduce to the next lowest daily and contact daily to reassess
- After a dose reduction, attempt to increase dose again as per protocol at the next scheduled visit to the Clinical Research Ward.

Intercurrent illness, if symptoms occur which are not temporally related to taking a dose (for example, but not limited to wheeze, rhinitis, vomiting, fever, diarrhoea or rash) occurring more that 2 hours after a dose then consider reducing dose and advise to seek medical consultation, contact daily to reassess. Subjects will have 24-hour access to the study team via a dedicated mobile telephone. There will also be a single email address checked daily Mon-Fri for non-urgent enquiries. The telephone duty will be rotated between [name], [name] and [name] on an equal basis. [name] and [name] will be able to contact [name] or [name] for further advice if needed. This system was used during the pilot study and proved helpful to the participants, but not over burdensome to the research team.

Peanut avoidance advice (waiting list control)

Provide written and verbal peanut avoidance advice. Advise complete peanut avoidance for five months until repeat oral challenge. Provide emergency medication as for active group and train in its use (together with emergency treatment plan).

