#### 9.2.2 Collection and recording of adverse events

Adverse events will be collected from the time the participant provides consent until the time the event resolves or until 30 days after the participant completes study treatment. Adverse events may be discovered through observing and questioning the participant or receiving an unsolicited complaint and questioning the participant in an objective manner. Throughout the study, the investigator will record all adverse events on the appropriate adverse event CRF regardless of their severity or relation to study medication or study procedure. The investigator will treat participants experiencing adverse events appropriately and observe them at suitable intervals until their symptoms resolve or their status stabilizes. SAEs will be recorded on the adverse event CRF and health authorities notified.

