#### 11.2 Endpoint analysis

**11.2.1 Analysis of primary endpoint**: The main analysis will compare the proportion of subjects who pass a peanut challenge in the intervention and control arms six-seven months after randomization, using a Fisher's exact test at the p<0.05 level of significance.

**11.2.2 Analysis of secondary endpoints**. Quality of life scores will be compared before and after intervention by pair wise comparison within individuals, and group medians will be compared using methods for non-parametric data. The results of cellular and humoral assessments of immune responses will be compared using methods for non-parametric data (e.g. comparison of medians of serum peanut specific IgG4 at different time points by Mann-Whitney U test). The incidence of adverse events will be compared between the intervention and control groups using a two-tailed Fisher's exact test at the p<0.05 level of significance. For package 2, the proportion of patients who may expect success will be calculated, with 95% confidence intervals. The influence of severity, age, sex, other allergy on immunotherapy success will be assessed by multiple logistic regression analysis.

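### The between-arm adverse-event comparison is confounded with ascertainment, because the diary, two-weekly visits and symptom-reporting advice are stated only within the immunotherapy procedures

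*Protocol*

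**What the plan says.** **Active arm (protocol 7.1).** "Every 2 weeks subjects return to the CRW for a dose increase and 1 hour of observation". A list of provisions opens "Provide each participating family with" and ends with the diary: "Subjects are asked to complete a symptom diary, noting type and duration of symptoms and any exacerbating factors". Families are advised to contact the team about any symptom at home. Once symptoms have occurred, several instructions add daily contact, for example "continue the current dose. Contact daily to reassess". Illness not related in time to a dose is covered as well.

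**Control arm (waiting-list paragraph of 7.1).** Families receive avoidance advice, and then: "Provide emergency medication as for active group and train in its use (together with emergency treatment plan". No diary, interim clinical visit or symptom-reporting advice is stated.

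**Both arms.** Section 9.2.2 collects events from consent and requires the investigator to record all of them, whatever their severity or relation to treatment. On how they come to light it says: "Adverse events may be discovered through observing and questioning the participant or receiving an unsolicited complaint". It fixes no interval and no common form of questioning. Section 3.3.9 places immune-profile samples at enrolment and at days 14, 75 and 150 in both arms.

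**Analysis.** Safety is a secondary endpoint (8.2). Section 11.2.2 says: "The incidence of adverse events will be compared between the intervention and control groups", using a two-tailed Fisher's exact test at 0.05.

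**The concern.** When events are found by observation, questioning and spontaneous report, the number found depends on how often someone asks and on whether the family keeps a written record. As section 7.1 is written, one arm has both supports and the other is promised neither. A difference in recorded incidence then combines two things: what immunotherapy does, and how much harder the trial looked in the treated arm.

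This matters most for two quantities. One is the incidence of events unrelated to dosing, such as ordinary childhood illness, where a spurious excess on treatment could appear. The other is the background of accidental reactions and emergency-medication use under avoidance, which a comparator arm is well placed to supply and for which no prospective record is specified. Unequal detection would make immunotherapy look worse than it is relative to avoidance. Analysis cannot later recover events that were never recorded.

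**Working it through.** **1. The plan's own figure.** The protocol gives no power or error figure for the adverse-event test. Its sample size is for the primary endpoint: 64% v 30%, Fisher's exact test, two-sided 0.05, 90% power, 49 per group (section 10). Exact enumeration at 49 per group gives power 0.906, and 98/0.95 = 103.2 rounds up to 104 recruited. Both reproduce. The sample size is not in question; it only supplies n = 104/2 = 52 per arm below.

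**2. Contacts stated before the second challenge.**

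| | Immunotherapy | Waiting list |
|---|---|---|
| Dosing visits | 9 dose steps, so 8 two-week intervals = 16 weeks, then at least 6 weeks on the final dose | none |
| Diary | stated, frequency not given | not stated |
| Advice to report home symptoms | stated | not stated |
| Daily contact | after symptoms only | not stated |
| Sampling time points | days 14, 75, 150 | days 14, 75, 150 |

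**3. Effect on the test for events unrelated to dosing.** Let the true incidence be p in both arms and the share of affected participants detected be s_A (active) and s_C (control). Recorded incidence is p·s_A v p·s_C. The rejection probability is the sum, over all pairs of counts (a, b), of Bin(a; 52, p·s_A) × Bin(b; 52, p·s_C), taken where the two-sided Fisher p-value is at most 0.05. The documents give no value for p, s_A or s_C. All are assumptions, with s_A = 1.

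| p | s_C | Recorded, active v control | Spurious difference | P(reject), 52 per arm |
|---|---|---|---|---|
| 50% | 100% | 50% v 50% | 0 points | 3.9% |
| 50% | 90% | 50% v 45% | 5 points | 6.5% |
| 50% | 75% | 50% v 37.5% | 12.5 points | 21.4% |
| 50% | 50% | 50% v 25% | 25 points | 70.3% |
| 30% | 75% | 30% v 22.5% | 7.5 points | 9.6% |
| 30% | 50% | 30% v 15% | 15 points | 37% |

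At 49 per arm and p = 50%, the figures for 100%, 75% and 50% control capture are 3.3%, 18.6% and 65.9%.

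**4. Effect on the test of all events.** Section 7.2 reports that about 70% of pilot participants had mild symptoms on therapy. Assume that rate, plus an independent 50% background in both arms. True incidence is then 1 − (0.30 × 0.50) = 85% on treatment v 50% in controls. With complete capture in both arms, Fisher's test already rejects in 96.3% of trials at 52 per arm. Unequal capture hardly changes that decision, but it changes the estimate: at 75% control capture the recorded contrast is 85% v 37.5%, so a true difference of 35 points is reported as 47.5.

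**The case against.** The strongest reply has five parts.

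- **The diary may not be active-only.** The list containing it opens "Provide each participating family with", and the waiting-list paragraph also sits inside 7.1. No sentence says controls keep no diary. This stands as a caution. Active-only is still the likelier reading: the list belongs to the immunotherapy procedures, its first item concerns the home dose, and the control paragraph restates medication, training and emergency plan, which would be needless if the list covered both arms.
- **Events are collected in both arms.** This stands. A reader might infer that control events go unrecorded. Section 9.2.2 does not support that: it requires all events to be recorded from consent, and controls have three sampling time points. What is missing is a common instrument and interval.
- **Daily calls are not surveillance.** This stands. Each is triggered by symptoms already known, so they add little to the first detection of an event.
- **The test would reject anyway.** This stands for all events together (step 4). A reader might infer from step 3 that the planned test will produce a false positive; that does not follow. The damage is to the size of the difference and what it means.
- **Detail can sit in the SAP.** This is true of which events enter the analysis, but not of what families are asked to record.

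It is also tempting to say that accidental reactions and adrenaline use are the events controls are least likely to report. The documents do not support that. Such events are memorable, and trivial symptoms may be likelier to be missed.

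**Conclusion.** The point holds as a design weakness in a secondary safety comparison. The protocol states more intensive event-finding for the immunotherapy arm, sets no common method, and then tests incidence between arms, so the estimated difference cannot be read as a treatment effect alone. It rests on reading the diary as active-only, which is likely but not explicit; the two-weekly visits differ between arms on any reading.

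The size cannot be known from the documents. Under the assumptions in step 3 it ranges from negligible (6.5% rejection at 90% control capture) to serious (70% at 50% capture) for events unrelated to dosing. For all events the significance verdict would probably be the same, and the distortion lies in the magnitude and in the background rate under avoidance. The primary endpoint, a double-blind challenge in both arms, is unaffected.

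A related inconsistency bears on observation time. The control paragraph says "Advise complete peanut avoidance for five months until repeat oral challenge", whereas section 5.1 gives six to seven months. These passages must be reconciled, because a shorter control window would add to the imbalance.

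**What to change.** 1. In the waiting-list paragraph of 7.1, state that these families keep the same symptom diary from allocation to the second challenge. In both arms, add lines for accidental peanut exposure and for use of antihistamine or adrenaline.
2. In 9.2.2, state that the diary is reviewed with the same set of questions in both arms at the existing day 14, 75 and 150 time points and at the second challenge.
3. In 11.2.2, base the formal between-arm comparison on events captured by that common diary and those common visits. Describe dose-related symptoms, and events found only at dosing visits or call-backs, within the active arm.

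If the diary was always meant for both arms, the first change simply makes that explicit.

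**Cost.** A short amendment and an existing form for about 52 more families, with no added visits. The downside is a modest diary burden on control families. Some difference in ascertainment will remain, because the trial is open-label and the treated arm will still be prompted at dosing visits; the report should say so.

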## 3.3.5 Active intervention and control group Peanut oral immunotherapy

Participants randomized to the active intervention arm will receive daily doses of peanut protein with two-weekly increments (see section 7). Participants will undergo six-seven months of immunotherapy before a second peanut challenge. Dose increments were well tolerated in our pilot study (achieved in 16/16) with no serious adverse events.

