#### Control group

We have added a control group. There are no data on resolution in severe peanut allergy. The allergy may resolve in up to 20% of mildly peanut allergic children. This is thought to happen slowly over a number of years, rather than the relatively short period of our study. The control group will undergo peanut avoidance for five months (current practice) during which time they are on the 'waiting list' before receiving active intervention. A recent study demonstrates precedent of using a waiting list control group: 45 children with egg and cow's milk allergy were randomised to waiting list control or oral immunotherapy. After 18-24 months all control group subjects had a positive food challenge, demonstrating persistence of their allergy. Subjects randomized to the control group will receive the current best management (peanut avoidance management plan) for six-seven months [in pilot duration was 58-210d (median 143d, mean 140d; about 5 months) n=12;]. This is provided using verbal and written information provision and training in the use of emergency medication and provision of an emergency treatment plan. In an ideal world, we would administer a placebo to participants in our control arm and this was considered in great detail during development work. The main reason for not including a placebo is the impossibility of being able to adequately blind an active or placebo snack. Importantly, in our open design pilot study 70% of children had reactions immediately after taking an active dose, meaning participating families (and the investigators) would quickly work out which arm of the study they were on. After development work, we also concluded that it was not possible to adequately mask larger doses of peanut protein in a snack size acceptable for a child to eat every day (800mg is the equivalent of 5-7 peanuts). An alternative would be to provide a peanut-flavored placebo snack, but it would be unethical to leave families on either arm in doubt as to whether oral tolerance had been induced or not. Families who falsely assume they are on the active treatment arm may relax their allergen avoidance practice, thereby putting their child at increased risk of a reaction. We feel that a placebo arm would also hamper recruitment and compliance. The obvious disadvantage of not including a placebo snack is that subjects will know which study arm they are assigned to. This is offset by the fact that the primary outcome (peanut allergy) will be diagnosed on the basis of an objective measure: double blind, placebo-controlled food challenge (DBPCFC), the gold-standard for food allergy diagnosis in research. On peanut challenge, neither the investigator, the nurse, nor the participant will know whether the participant's dose is peanut or placebo, so it will be impossible for the outcome of the challenge to be influenced by that knowledge.

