#### 9.1.1 Challenge timing

All participants will undergo a DBPCFC at enrolment (we expect the majority to react during this) After six-seven months the active and control group subjects undergo a second DBPCFC. The control group will then undergo immunotherapy, after six-seven months they also undergo a final DBPCFC.

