#### 12. Ethical arrangements

We obtained ethical consent for our pilot study which had an identical design to the active intervention arm of this proposal. We have the additional consideration of the control group in this proposal. Subjects in the control group will undergo a peanut challenge before and after a six-seven month period of current best management. Therefore these subjects will not be disadvantaged by comparison with current best standards of treatment, we have the best published outcome for peanut allergy.

Subjects will be provided with an information sheet that will be approved by the Cambridge LREC, describing the potential benefits and risks of participation. We will then offer to meet the families for further discussion. Informed consent will be obtained from parents for children (<16y). Ethical approval will be considered by the Cambridgeshire 2 LREC on 25tht September 2009.

**13. Research Governance** This study will be conducted using good clinical practice (GCP), as delineated in the MRC Guidelines on Good Clinical Practice in Clinical Trials. Before initiation, the protocol and the informed consent documents will be reviewed and approved by our local ethics committee. The study will be sponsored by University of Cambridge Clinical School (Dept Medicine). The study may be inspected by the University under their remit as sponsor to ensure adherence to Good Clinical Practice.

In accordance with the Research Governance Framework we will nominate a trial steering committee (TSC). An independent chair will be appointed and membership will include [name], [name], [name] and [name] (trial statistician), it will also include one independent clinician and [name], of the Anaphyalxis Campaign (founder and recent chief executive). The TSC has responsibility for strategy and direction and has the responsibility of ensuring the project's aims are delivered on time. The TSC will invite EME program members to attend and report directly to the EME. We will also convene a Data Monitoring Committee (DMC) which will comprise one statistician and two independent clinicians. The DMC will report to the TSC and also report any serious adverse events directly to the EME program

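### Section 7.1 sends controls to their repeat challenge at five months, while the design, challenge schedule and primary analysis set six to seven months for both arms

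*Protocol*

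**What the plan says.** The protocol dates the control arm's second challenge in several places, and they do not agree.

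**Five months.** The control-arm advice at the end of section 7.1 reads "Advise complete peanut avoidance for five months until repeat oral challenge". Section 3.3.5 says "The control group will undergo peanut avoidance for five months (current practice". Section 3.3.2 refers the natural-resolution rate used for power to a waiting period of the same length.

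**Six to seven months.** Section 5.1 gives controls best current management "for six-seven months followed by DBPCFC". Section 9.1.1 says "After six-seven months the active and control group subjects undergo a second DBPCFC". Section 11.2.1 compares the proportions who "pass a peanut challenge in the intervention and control arms six-seven months after randomization". Section 12 says "Subjects in the control group will undergo a peanut challenge before and after a six-seven month period of current best management". A later sentence of 3.3.5 also gives controls six to seven months.

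**Active arm.** Section 3.3.5 says "Participants will undergo six-seven months of immunotherapy before a second peanut challenge". Section 7.1 says the final dose "is taken for at least six weeks until six-seven months post randomization when a DBPCFC is performed".

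**Primary endpoint.** Section 8.1 dates the challenge at six months, which matches neither wording exactly.

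**The concern.** The five-month figure is not confined to background text. It stands in the instruction that staff would use to advise control families and book the visit that yields the primary outcome. A team following it would assess the two arms at different times after randomization, with controls outside the window set in 11.2.1.

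The direction of any bias is known. A control passes the second challenge mainly if the allergy has resolved, and a shorter wait leaves less time for that. An early control challenge therefore lowers the control pass rate and enlarges the apparent effect of immunotherapy. Section 3.3.5 adds the control group because resolution in severe allergy is undocumented, and it offers the blinded challenge as the safeguard for an open-label comparison. Both arguments need the arms to be challenged at the same time.

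The error could not be repaired later. Under 3.3.5, controls who are still allergic are offered immunotherapy after their second challenge, so no untreated six-to-seven-month result could then be obtained from them.

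**Working it through.** **1. The plan's own figure.** Inputs from section 10: Fisher's exact test, two-sided 0.05, 64% vs 30%, 49 per group. Full binomial enumeration gives power of 0.906, against a stated 90%. For recruitment, 2 × 49 = 98 and 98 / 0.95 = 103.2, which rounds up to 104; equivalently, 1 − 98/104 = 5.8%, the stated loss of just over 5%. The sample size reproduces.

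**2. Could five months be the common time point?** The dose list in 7.1 has nine steps, so eight two-week increments: 8 × 2 = 16 weeks. Adding at least six weeks on the final dose gives 22 weeks, or 154 days; 154 / 30.44 = 5.06 months. Even the shortest full course slightly exceeds five months, and 7.1 fixes the active challenge at six to seven months anyway. Five months is therefore the outlier.

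**3. Gap between arms under 7.1.** 6 − 5 = 1 month to 7 − 5 = 2 months.

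**4. Size of the bias.** The protocol gives no resolution rate per unit time. Sections 3.3.2 and 3.3.5 say only that at most 20% resolve, among mildly allergic children, over years. *Assumption:* 20% resolve over T months at a constant rate, with T = 24, 36 or 60. The proportion resolved by month t is r(t) = 1 − 0.8^(t/T). The inflation of the difference is r(6) − r(5) to r(7) − r(5).

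| T (months) | r(5) | r(6) | r(7) | Inflation (points) | Of 49 controls |
|---|---|---|---|---|---|
| 24 | 4.54% | 5.43% | 6.30% | 0.88 to 1.76 | 0.43 to 0.86 |
| 36 | 3.05% | 3.65% | 4.25% | 0.60 to 1.19 | 0.29 to 0.59 |
| 60 | 1.84% | 2.21% | 2.57% | 0.36 to 0.73 | 0.18 to 0.36 |

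The planned difference is 64 − 30 = 34 points. The inflation is about 0.4 to 1.8 points, or less than one control participant.

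**The case against.** The strongest reply is that the intended design is plain. Section 9.1.1 is the section on challenge timing, it names both arms, and the design, primary analysis and ethics sections agree with it. A team that books visits from 9.1.1 creates no asymmetry. Figure 1, which the protocol also cites for the flow of challenges, is not available here. Even if 7.1 were followed, the effect is below one participant, and the 20% behind that estimate belongs to mild allergy, whereas this trial deliberately includes severe cases.

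Most of this stands. The intended window is clear and the numerical effect is small. But 7.1 is where the delivery of the control arm is described, and it sets a different date for that arm's primary-outcome visit. That another section has it right does not make the instruction harmless.

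Two stronger readings are tempting, and the document supports neither.

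- *The trial is underpowered.* Because 3.3.2 ties the 30% control rate to five months, a reader might infer that the rate is higher by six to seven months and that power falls below 90%. That treats 30% as a true five-month rate. At a constant rate it would imply 1 − 0.7^(12/5) = 57.5% resolved within a year, which conflicts with the protocol's account of slow resolution over years. Section 3.3.2 presents 30% as conservative and expects well under 20%. At a 20% control rate, exact power is already 99.3%.
- *The milestone table settles the waiting period.* A reader might try to read a six-month wait from Table 2. Its first block, as read from the PDF, has 16 dates for 15 milestones, so the pairing is unreliable and nothing here rests on it.

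**Conclusion.** This is an internal inconsistency in the timing of the primary endpoint, and it should be corrected. It is not a sample size error, and it does not show that the trial's result would be biased in practice. If 7.1 were followed, controls would be challenged one to two months early and outside the 11.2.1 window, and any bias would favour immunotherapy. The estimate of 0.4 to 1.8 points rests on the assumption of 20% resolution over two to five years at a constant rate; slower resolution, as the protocol expects for these patients, makes it smaller. The case for correction is that the conflicting text governs the primary-outcome visit in one arm of an open-label trial and that the error would be irreversible after crossover.

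**What to change.** - In 7.1, 3.3.2 and the first sentence of 3.3.5 on the control period, replace five months with six to seven months post randomization, to match 5.1, 9.1.1, 11.2.1 and 12.
- In 8.1, replace the six-month time point with the same six-to-seven-month window, so that the endpoint definition and its analysis agree.
- In 3.3.2, state that the conservative 30% control pass rate applies to that window. This re-dates a planning assumption, and it is defensible because the protocol expects well under 20% even over a longer period.

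The cost is a few words in four sections and one added sentence. No visits, procedures or participants are added. The test, the 90% power, 49 per group and N = 104 stay as they are.
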